5.3.5.9 Lack of Efficacy or Worsening of Breast Cancer

Events that are clearly consistent with the expected pattern of progression of the underlying disease should not be recorded as adverse events. These data will be captured as efficacy assessment data only. In most cases, the expected pattern of progression will be based on mRECIST. In rare cases, the determination of clinical progression will be based on symptomatic deterioration. However, every effort should be made to document progression through use of objective criteria. If there is any uncertainty as to whether an event is due to disease progression, it should be reported as an adverse event.

5.3.5.10 Hospitalization or Prolonged Hospitalization

Any adverse event that results in hospitalization (i.e., inpatient admission to a hospital) or prolonged hospitalization should be documented and reported as a serious adverse event (per the definition of serious adverse event in Section [5.2.2](#)), except as outlined below.

An event that leads to hospitalization under the following circumstances should not be reported as an adverse event or a serious adverse event:

- Hospitalization for respite care

- Hospitalization for a preexisting condition, provided that all of the following criteria are met:

The hospitalization was planned prior to the study or was scheduled during the study when elective surgery became necessary because of the expected normal progression of the disease.

The patient has not experienced an adverse event.

- Hospitalization due solely to progression of the underlying cancer

An event that leads to hospitalization under the following circumstances is not considered to be a serious adverse event, but should be reported as an adverse event instead:

- Hospitalization that was necessary because of patient requirement for outpatient care outside of normal outpatient clinic operating hours

5.3.5.11 Cases of Overdose, Medication Error, Drug Abuse, or Drug Misuse

Overdose (accidental or intentional), medication error, drug abuse, and drug misuse (hereafter collectively referred to as “special situations”), are defined as follows:

- Accidental overdose: accidental administration of a drug in a quantity that is higher than the assigned dose
- Intentional overdose: intentional administration of a drug in a quantity that is higher than the assigned dose
- Medication error: accidental deviation in the administration of a drug

In some cases, a medication error may be intercepted prior to administration of the drug.

- Drug abuse: intentional excessive use of a drug that may lead to addiction or dependence, physical harm, and/or psychological harm
- Drug misuse: intentional deviation in the administration of a drug that does not qualify as drug abuse

In cases where drug is to be self-administered by the patient, drug misuse could involve the drug being administered to someone other than the patient.

Special situations are not in themselves adverse events, but may result in adverse events. Each adverse event associated with a special situation should be recorded separately on the Adverse Event eCRF. If the associated adverse event fulfills seriousness criteria, the event should be reported to the Sponsor immediately (i.e., no more than 24 hours after learning of the event; see Section 5.4.2). For GDC-9545 adverse events associated with special situations should be recorded as described below for each situation:

- Accidental overdose: Enter the adverse event term. Check the “Accidental overdose” and “Medication error” boxes.

- Intentional overdose: Enter the adverse event term. Check the “Intentional overdose” box. If drug abuse is suspected, check the “Drug abuse” box. If drug abuse is not suspected, check the “Drug misuse” box.
- Medication error that does not qualify as an overdose: Enter the adverse event term. Check the “Medication error” box.
- Medication error that qualifies as an overdose: Enter the adverse event term. Check the “Accidental overdose” and “Medication error” boxes.
- Drug abuse that does not qualify as an overdose: Enter the adverse event term. Check the “Drug abuse” box.
- Drug abuse that qualifies as an overdose: Enter the adverse event term. Check the “Intentional overdose” and “Drug abuse” boxes.
- Drug misuse that does not qualify as an overdose: Enter the adverse event term. Check the “Drug misuse” box.
- Drug misuse that qualifies as an overdose: Enter the adverse event term. Check the “Intentional overdose” and “Drug misuse” boxes.

In addition, all special situations associated with GDC-9545, regardless of whether they result in an adverse event, should be recorded on the Adverse Event eCRF as described below:

- Accidental overdose: Enter the drug name and “accidental overdose” as the event term. Check the “Accidental overdose” and “Medication error” boxes.
- Intentional overdose: Enter the drug name and “intentional overdose” as the event term. Check the “Intentional overdose” box. If drug abuse is suspected, check the “Drug abuse” box. If drug abuse is not suspected, check the “Drug misuse” box.
- Medication error that does not qualify as an overdose: Enter the name of the drug administered and a description of the error (e.g., wrong dose administered, wrong dosing schedule, incorrect route of administration, wrong drug, expired drug administered) as the event term. Check the “Medication error” box.
- Medication error that qualifies as an overdose: Enter the drug name and “accidental overdose” as the event term. Check the “Accidental overdose” and “Medication error” boxes. Enter a description of the error in the additional case details.
- Intercepted medication error: Enter the drug name and “intercepted medication error” as the event term. Check the “Medication error” box. Enter a description of the error in the additional case details.
- Drug abuse that does not qualify as an overdose: Enter the drug name and “drug abuse” as the event term. Check the “Drug abuse” box.
- Drug abuse that qualifies as an overdose: Enter the drug name and “intentional overdose” as the event term. Check the “Intentional overdose” and “Drug abuse” boxes.
- Drug misuse that does not qualify as an overdose: Enter the drug name and “drug misuse” as the event term. Check the “Drug misuse” box.

- Drug misuse that qualifies as an overdose: Enter the drug name and “intentional overdose” as the event term. Check the “Intentional overdose” and “Drug misuse” boxes.
- Drug administered to someone other than the patient: Enter the drug name and “patient supplied drug to third party” as the event term. Check the “Drug misuse” box.

As an example, an accidental overdose that resulted in a headache would require two entries on the Adverse Event eCRF, one entry to report the accidental overdose and one entry to report the headache. The “Accidental overdose” and “Medication error” boxes would need to be checked for both entries.

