4.3 STUDY TREATMENT AND OTHER TREATMENTS RELEVANT TO THE STUDY DESIGN

The investigational medicinal products (IMPs) for this study are GDC-9545, anastrozole, and palbociclib.

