4.3.2 Study Treatment Dosage, Administration, and Compliance

The treatment regimens are summarized in Section 3.1 and outlined in [Figure 1](#) and [Figure 2](#).

[figure not shown]
Refer to the pharmacy manual for detailed instructions on drug preparation, storage, and administration.

To assess patient compliance with self-administration of study medication (GDC-9545, anastrozole, and palbociclib), site study staff will provide patients with detailed instructions and training for the handling and administration of study drugs. Patients will receive and should be instructed to complete a medication diary. Patients will be instructed to bring all unused study medication and their medication diaries to the clinic at specified study visits (see schedule of activities [Appendix 1](#)). Compliance will be assessed by investigator site team staff (e.g., by counting returned tablets/ capsules, clinic visit patient interview notes, and reviewing patient diaries).

Details on treatment administration should be noted on the Study Drug Administration electronic Case Report Form (eCRF). Cases of overdose, medication error, drug abuse, or drug misuse, along with any associated adverse events, should be reported as described in Section [5.3.5.11](#).

Guidelines for dosage modification and treatment interruption, or discontinuation for patients who experience adverse events are provided in Section [5.1.4](#).

Figure 2 Study Treatment Regimens

C = cycle; D = day.

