6.5.1 Analyses of Exposure, Adverse Event, Laboratory, and Vital Sign Data

The frequency, nature, and severity of treatment-emergent adverse events, adverse events leading to death, adverse events leading to study drug discontinuation and dose modification, serious adverse events, and adverse events of special interest will be summarized by treatment arm. All deaths will be summarized. Selected laboratory data will be summarized by treatment received and grade compared with baseline, and measurements outside of the normal range will be identified. Relevant vital signs will be presented using summary statistics by treatment received. Drug exposure will also be summarized, including duration of treatment, cumulative dose, and dose intensity.

Treatment-emergent adverse events are defined as adverse events that occur after the first dose of study treatment. Adverse events will be summarized by mapped MedDRA preferred terms and appropriate MedDRA hierarchy. Adverse event severity will be graded according to NCI CTCAE v5.0. Multiple occurrences of the same event will be counted once at the maximum severity.

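### Stand-alone overdose and medication-error entries on the Adverse Event eCRF are required for GDC-9545 only, and no rule keeps them out of the comparison of adverse events between arms

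*Combined protocol and SAP*

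**What the plan says.** Section 4.3 states: "The investigational medicinal products (IMPs) for this study are GDC-9545, anastrozole, and palbociclib". Section 4.3.2 covers patient handling of all of them: "To assess patient compliance with self-administration of study medication (GDC-9545, anastrozole, and palbociclib), site study staff will provide patients with detailed instructions". The same section then directs: "Cases of overdose, medication error, drug abuse, or drug misuse, along with any associated adverse events, should be reported as described in Section" 5.3.5.11. That direction names no drug.

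Section 5.3.5.11 works in three layers.

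- General rules, with no drug named. "Special situations are not in themselves adverse events, but may result in adverse events", and "Each adverse event associated with a special situation should be recorded separately on the Adverse Event eCRF".
- Check-box instructions for adverse events that follow a special situation, limited to one drug: "For GDC-9545 adverse events associated with special situations should be recorded as described below for each situation".
- Stand-alone entries, made even if the patient comes to no harm, limited to the same drug: "all special situations associated with GDC-9545, regardless of whether they result in an adverse event, should be recorded on the Adverse Event eCRF". The event term is then the overdose, error, misuse or abuse itself.

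The section ends with a worked example in which an overdose leading to a headache produces two entries. The example names no drug.

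On analysis, Section 6.5.1 says: "Adverse events will be summarized by mapped MedDRA preferred terms and appropriate MedDRA hierarchy". It counts as treatment-emergent any adverse event after the first dose, summarizes by treatment arm, and says nothing about special-situation entries.

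**The concern.** The safety objective in Section 2.2 compares the incidence and severity of adverse events between GDC-9545 plus palbociclib and anastrozole plus palbociclib, in an open-label trial. That comparison needs the same recording rule in both arms. Here the rule for one kind of entry depends on the drug, and the drug is what distinguishes the arms.

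The entries share a form with real adverse events, and the analysis section does not say how to separate them. At stake are a small artificial excess in the experimental arm's overall adverse event count, and overdose or error terms that appear in one arm for reasons of recording alone. There is also a consistency problem across about 90 sites. One site may follow the worked example and enter a palbociclib or anastrozole overdose, while another follows the GDC-9545 limitation and does not.

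**Working it through.** The plan has no figure to reproduce on this point, so the check sets the sections side by side.

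| What is recorded | GDC-9545 (experimental arm) | Anastrozole (control arm) | Palbociclib (both arms) |
|---|---|---|---|
| Adverse event resulting from a special situation (5.3.5.11) | Yes | Yes | Yes |
| Special-situation check boxes on that adverse event (5.3.5.11) | Yes | No instruction | No instruction |
| Stand-alone entry, harm or no harm (5.3.5.11) | Yes | No instruction | No instruction |
| Study Drug Administration eCRF, diary, pill counts (4.3.2, 4.3.2.2) | Yes | Yes | Yes |
| Protocol deviation documented (9.2); major ones summarized by arm (6.2) | Yes | Yes | Yes |

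**Where the arms differ.** Rows two and three separate GDC-9545 from anastrozole, so those rows depend on the arm. The palbociclib column applies equally to both arms, so its gaps create no imbalance.

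**Whether the difference reaches the tables.** A stand-alone GDC-9545 entry after the first dose sits on the Adverse Event eCRF with an event term. Section 5.3.5.11 says it is not an adverse event. Section 6.5.1 neither repeats that nor excludes it. The outcome depends on how the tables are programmed, which the plan leaves open.

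**Which summaries could move.** Such an entry would appear under its own overdose or error term, so it would not add to nausea, bradycardia or neutropenia. An error without consequence would not be expected to enter the serious, Grade 3 or higher, special-interest or discontinuation summaries. That leaves the overall count and the overdose or error terms.

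**Size, on assumed rates.** The documents give no rate of special situations, so this is an illustration only.

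- Patients per arm: 215 / 2 = 107.5, taken as 107.
- Experimental-arm patients with a stand-alone entry, if the rate per patient is r: 107 × 0.01 = 1.1; 107 × 0.05 = 5.4; 107 × 0.10 = 10.7. That is about 1, 5 or 11.
- Control-arm patients with such an entry for their own endocrine drug: 0 at the same error rate.

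The proportion with any adverse event rises only through patients who have no other event. If a share q has another event, and errors are independent of other events, the rise is r × (1 − q). Section 1.4.2 reports neutropenia in 67% of patients on GDC-9545 100 mg plus palbociclib. Using q = 0.67 as a rough floor (another GDC-9545 dose, and advanced disease):

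- r = 1%: 0.01 × 0.33 = 0.3 percentage points
- r = 5%: 0.05 × 0.33 = 1.7 percentage points
- r = 10%: 0.10 × 0.33 = 3.3 percentage points

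A higher q makes each of these smaller.

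**The case against.** The best defence has three parts. First, fuller reporting for GDC-9545 is a reasonable sponsor choice: Section 5.1 describes it as unapproved, while safety information for the other two drugs is referenced to existing product documents. Second, since special situations are declared not to be adverse events, a summary of adverse events would naturally leave them out, and the check boxes already allow this. Third, Section 4.3.2 need not conflict with Section 5.3.5.11, which can be read as general rules plus additions for one drug.

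Much of this stands. Bias is possible, not certain, and the choice of scope can be defended. It does not settle the point, because the plan puts declared non-events on the adverse event form in one arm and never says to take them out.

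A reader might infer more than the documents support, in four ways.

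- *That anastrozole and palbociclib dosing errors go unrecorded.* Dosing eCRFs, diaries, accountability logs and deviation records cover all three drugs, and resulting adverse events are recorded for any drug. What is missing is the explicit special-situation entry. Those sources are only a partial substitute: net counts of units dispensed and returned may not show a double dose offset by a missed one, or an intercepted error.
- *That the control arm can never have such an entry.* Giving the wrong drug is a listed error, so a control patient given GDC-9545 by mistake would also need one.
- *That leaving out palbociclib biases the comparison.* It is given in both arms under the same rule, so its omission is a gap in completeness.
- *That a large share of the experimental arm would be affected.* No error rate is given, so any large figure would come wholly from the rate assumed.

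**Conclusion.** The point holds as a minor one. The stand-alone entry rule and its check boxes apply to GDC-9545 only, which makes one kind of record on the Adverse Event eCRF depend on the arm, and Section 6.5.1 does not neutralize it. The reference in Section 4.3.2 and the worked example, neither limited by drug, leave sites unsure what to enter for the other two products.

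The likely effect is small and limited to the overall adverse event count and to overdose or error terms. The 1, 5 or 11 patients of 107 rest on assumed rates of 1%, 5% and 10%, and whether they enter the tables at all rests on programming that the plan does not specify. The primary endpoint and the efficacy analyses are not touched. The change is worth making as a cheap improvement.

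**What to change.** In Section 5.3.5.11, apply both lists (check boxes on resulting adverse events, and stand-alone entries) to any study treatment, naming GDC-9545, anastrozole and palbociclib. The worked example then fits without change, and the reference from Section 4.3.2 leads to an instruction for every drug.

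In Section 6.5.1, add that special-situation entries are tabulated separately by arm and excluded from treatment-emergent adverse event counts, while adverse events resulting from them stay in. If the sponsor prefers to keep the fuller reporting for GDC-9545 alone, this sentence by itself protects the between-arm comparison.

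The cost is amendment wording, a filter on existing check boxes in the adverse event programs, and slightly more data entry for two drugs.

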5.3.5.12 Patient-Reported Outcome Data

Adverse event reports will not be derived from PRO-CTCAE or other PRO data by the Sponsor. In addition, the Sponsor will make no attempt to reconcile patient reports of treatment-related symptoms (via PRO-CTCAE) with investigator reports of adverse events. Sites are not expected to review the PRO-CTCAE or other PRO data for adverse events.

5.3.5.13 Safety Biomarker Data

Adverse event reports will not be derived from safety biomarker data by the Sponsor, and safety biomarker data will not be included in the formal safety analyses for this study. In addition, safety biomarker data will not inform decisions on patient management.

5.4 IMMEDIATE REPORTING REQUIREMENTS FROM INVESTIGATOR TO SPONSOR

Certain events require immediate reporting to allow the Sponsor to take appropriate measures to address potential new risks in a clinical trial. The investigator must report such events to the Sponsor immediately; under no circumstances should reporting take place more than 24 hours after the investigator learns of the event. The following is a list of events that the investigator must report to the Sponsor within 24 hours after learning of the event, regardless of relationship to study drug:

- Serious adverse events (defined in Section 5.2.2; see Section 5.4.2 for details on reporting requirements)
- Adverse events of special interest (defined in Section 5.2.3; see Section 5.4.2 for details on reporting requirements)
- Pregnancies (see Section 5.4.3 for details on reporting requirements)

For serious adverse events and adverse events of special interest, the investigator must report new significant follow-up information to the Sponsor immediately (i.e., no more than 24 hours after becoming aware of the information). New significant information includes the following:

- New signs or symptoms or a change in the diagnosis

- Significant new diagnostic test results
- Change in causality based on new information
- Change in the event's outcome, including recovery
- Additional narrative information on the clinical course of the event

Investigators must also comply with local requirements for reporting serious adverse events to the local health authority and IRB/EC.

5.4.2 Reporting Requirements for Serious Adverse Events and Adverse Events of Special Interest

5.4.2.1 Events That Occur prior to Study Drug Initiation

After informed consent has been obtained but prior to initiation of study drug, only serious adverse events caused by a protocol-mandated intervention should be reported. The paper Clinical Trial Serious Adverse Event/Adverse Event of Special Interest Reporting Form provided to investigators should be completed and submitted to the Sponsor or its designee immediately (i.e., no more than 24 hours after learning of the event), either by faxing or by scanning and emailing the form using the fax number or email address provided to investigators.

5.4.2.2 Events That Occur after Study Drug Initiation

After initiation of study drug, all serious adverse events and adverse events of special interest will be reported until 28 days after the final dose of study treatment. Investigators should record all case details that can be gathered immediately (i.e., within 24 hours after learning of the event) on the Adverse Event eCRF and submit the report via the electronic data capture (EDC) system. A report will be generated and sent to Roche Safety Risk Management by the EDC system.

In the event that the EDC system is unavailable, the paper Clinical Trial Serious Adverse Event/Adverse Event of Special Interest Reporting Form provided to investigators should

be completed and submitted to the Sponsor or its designee immediately (i.e., no more than 24 hours after learning of the event), either by faxing or by scanning and emailing the form using the fax number or email address provided to investigators. Once the EDC system is available, all information will need to be entered and submitted via the EDC system.

Instructions for reporting serious adverse events that occur until 28 days after the final study treatment are provided in Section 5.6.

5.4.3 Reporting Requirements for Pregnancies

5.4.3.1 Pregnancies in Female Patients

Only postmenopausal female patients are permitted in the study. Patients will be instructed to immediately inform the investigator if they become pregnant during the study or within 28 days after the final dose of study drug. A paper Clinical Trial Pregnancy Reporting Form should be completed and submitted to the Sponsor or its designee immediately (i.e., no more than 24 hours after learning of the pregnancy), either by faxing or by scanning and emailing the form using the fax number or email address provided to investigators. Pregnancy should not be recorded on the Adverse Event eCRF. The investigator should discontinue study drug and counsel the patient, discussing the risks of the pregnancy and the possible effects on the fetus. Monitoring of the patient should continue until conclusion of the pregnancy. Any serious adverse events associated with the pregnancy (e.g., an event in the fetus, an event in the mother during or after the pregnancy, or a congenital anomaly/birth defect in the child) should be reported on the Adverse Event eCRF. In addition, the investigator will submit a Clinical Trial Pregnancy Reporting Form when updated information on the course and outcome of the pregnancy becomes available.

